FP is obtained from donated whole blood and contains all enzymatic coagulation factors, although some coagulation factor activity is lost during storage and processing (including freezing for storage and thawing prior to transfusion) [28]. FP utilised in North America is not commonly pathogen-reduced. FP is the mainstay of therapy for bleeding cardiac surgery patients requiring coagulation factor replacement in many countries and is administered in around 15% of all cardiac surgeries in the United States [29]. Despite being a mainstay of therapy, there is limited clinical trial evidence on the use of FP in bleeding cardiac surgery patients requiring coagulation factor replacement [30]. Nevertheless, it is recommended by current guidelines and is considered standard practice to transfuse FP in bleeding patients who have coagulation factor deficiency, as indicated by an elevated international normalised ratio (INR) >1.5 , which indicates that one or more coagulation factor levels are below the 30% critical threshold [31-37].

The widespread use of FP needs to be considered in the context of the risks associated with its use [38, 39]. FP can cause serious adverse events (SAEs) including allergic reactions (which occur in 1-3% of transfusions, ranging from mild to life-threatening

anaphylaxis) [30]; transfusion-related acute lung injury (TRALI), which is a leading cause of transfusion-related death [30, 40]; and transfusion-associated circulatory overload (TACO), which occurs in approximately 5% of transfusions as a result of the large volume of transfusion (10–15 mL/kg) that is required to achieve therapeutic effect with FP [41]. FP transfusion can also lead to transmission of infectious diseases, as FP is not usually filtered or treated with solvent/detergent [42]. These adverse effects are often dose-dependent [43–46]. Another important consideration with FP use is that it requires ABO blood group compatibility matching and thawing, which can delay therapy. The large volumes of FP needed to achieve therapeutic effect can further delay time to haemostatic control and lead to substantial haemodilution, resulting in additional RBC transfusions [47]. Therefore, although FP is currently a mainstay of therapy in North America, due to the disadvantages and risks associated with its use, it could be considered to be an unsatisfactory treatment.

Prothrombin Complex Concentrate (PCC)

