10. Comparison of the incidence of intracerebral haemorrhage during the first 24 hours after start of surgery, after the end of CPB and after IMP initiation between the *Octaplex* and FP groups.
11. Comparison of the incidence of gastrointestinal haemorrhage during the first 24 hours after start of surgery, after the end of CPB and after IMP initiation between the *Octaplex* and FP groups.
12. Comparison of the incidence of surgical re-exploration during the first 24 hours after start of surgery, after the end of CPB and after IMP initiation between the *Octaplex* and FP groups.
13. Comparison of the change in INR, from within 30 minutes before to within 60 minutes after the initiation of IMP administration, between the *Octaplex* and FP groups; INR reduction will be considered successful if the magnitude of the reduction is >1.0 or the post-treatment level drops below 1.5.
14. Comparison of the changes in other coagulation parameters, including PT, aPTT, fibrinogen activity, ROTEM EXTEM CT and MCF, ROTEM FIBTEM MCF and platelets, from within 75 minutes before to within 75 minutes after the initiation of IMP administration, between the *Octaplex* and FP groups.
15. Comparison of time elapsed from initiation of the first dose of IMP to arrival into the ICU between the *Octaplex* and FP groups.

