¹ In general, the initial protamine dose should not exceed 400 mg, irrespective of amount of heparin given. If an additional protamine dose does not shorten ACT, consider low fibrinogen levels or deficiency of enzymatic coagulation factors as a reason for prolonged ACT and treat according to the algorithm.

² BSS < 2 (less than moderate) = no therapy; BSS 2-3 (moderate-severe) = institute stepwise treatment; assess bleeding after each product; BSS 4 (life threatening) = administer therapy as necessary **without** waiting for laboratory results and combine therapies as appropriate.

³ POC-INR should be performed >10–15 minutes after protamine or results may be inaccurate.

ACT = activated clotting time; Blwk = bloodwork; BSS, bleeding severity scale; CBC = complete blood count; POC = point-of-care; CPB = cardiopulmonary bypass; CT = clotting time; IMP = investigational medicinal product; INR, international normalised ratio;

Standard and point-of-care coagulation measures will be obtained as per usual clinical practice, ideally within 75 minutes before and after each IMP administration.

All AEs and SAEs occurring until POD-30 will be recorded. Patients will be followed by research coordinators in each institution. All clinical outcomes will be obtained from patients' medical records and electronic records, history and physical where needed and via phone contact during the follow-up visits.

The flow chart of assessments by study visit is given in **Table 1**.

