7.3.6.2 Local Laboratory

Table 6 summarises all test parameters performed as part of standard of care, the results of which will be collected as available.

Table 6 Test Parameters and Laboratories

Test	Material needed	Responsible Laboratory
Coagulation profile		
Point-of-care INR	Fresh blood	Local
(PT, aPTT, INR, fibrinogen activity via Clauss assay)	Citrated blood	Local
*ROTEM EXTEM CT	Citrated blood	Local
*ROTEM EXTEM MCF	Citrated blood	Local
*ROTEM FIBTEM MCF	Citrated blood	Local
PlateletWorks		
Haematology – standard panel as per local lab	Citrated blood	Local
Clinical chemistry – standard panel as per local lab	Serum	Local
Safety laboratory analyses		
Troponin	Serum	Local
ALT/ALP	Serum	Local
Bilirubin	Serum	Local
Creatinine	Serum	Local

ALT, alanine aminotransferase; ALP, alkaline phosphatase; CT, clotting time; MCF, maximum clot firmness; PT, prothrombin time; aPTT, activated partial thromboplastin time; ROTEM, thromboelastometry

*ROTEM or TEG can be measured

The haemoglobin and INR measurements will be performed at preestablished time points (**Table 7**).

Table 7 Mandatory Test Parameters and Laboratories

Test	Material needed	Responsible laboratory
Coagulation profile		
Point-of-care INR	Fresh blood Citrated blood	Local Local
Haematology		
Haemoglobin	Citrated blood	Local

Blood Sampling

All blood sampling will be performed as per standard practice at the local institution.

The *actual* time of blood sampling will be recorded. If the draw time is not recorded for samples processed in the laboratory, the draw time will be estimated based on the received time in the laboratory minus 10 minutes. For ROTEM and PlateletWorks, if the exact draw time is not recorded, the time for start of testing will be used for draw time.

Citrated and Fresh Blood

Citrated and fresh blood as required by the local laboratory will be collected and processed in accordance with local requirements.

Serum

Serum will be obtained for the determination of clinical chemistry, haematology, and safety labs (ALT, ALP, creatinine, bilirubin, troponin), where a serum blood sample has been collected.

Recording of Clinically Significant Abnormal Laboratory Values as AEs/ADRs

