### Canadian Study Sites:

At the Canadian study sites, informed consent will be obtained from the patient or the patient's legally authorised representative (LAR) as soon as possible after surgery. If neither the patient nor the LAR is reachable for consent during the follow-up period, a family member who is not a LAR is to be provided with an opportunity to object to the patient's participation in the study.

Due to the emergency nature of the condition being studied (i.e., bleeding during surgery) the trial will include only patients who are incapable of providing informed consent at the time the therapy is needed and in whom delays in obtaining surrogate consent can be severely detrimental to their well-being. Thus, this study qualifies for alteration to consent requirement before randomisation, in accordance with Article 3.7A of the 2018 Tri-Council Policy Statement on the Ethical Conduct for Research Involving Humans. Patient or LAR consent from all patients, including those untreated, will be obtained at the earliest possible opportunity after surgery.

It is not possible to predict which patients will bleed due to coagulation factor deficiency, and once identified, any delays in therapy will lead to patient harm. The entire process from termination of CPB to administration of the blood products is around 50 minutes. However, the time frame for therapy decision, and consequently for seeking consent from a LAR for the patient to participate in the trial (meaning consent to randomisation and all study procedures thereafter), is even shorter, as it consists of the 5–10 minutes in which coagulation assays are reviewed and a call is placed to the blood bank to order coagulation factors. Even if it were possible to contact a LAR to seek consent during this time, the acuity of the situation would likely be highly stressful to the LAR, which could preclude them from effectively making an informed decision regarding consent. These factors make it essentially impossible to obtain prospective informed consent from a LAR during the surgery.

As a rule, only data from randomised and treated patients with informed consent will be analysed. Consented and randomised but untreated patients will not be included in the efficacy or safety analyses but will be followed for 30 days to determine between-group comparability in baseline characteristics and outcomes.

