## 7.1. Conventions

### 7.1.1. Baseline definition

Baseline will be defined as the last value on or prior to the first IMP administration.

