- S9. Comparison of the incidence of administration of non-IMP coagulation factor products – including fibrinogen concentrate and activated recombinant factor VII – during the first 24 hours and 7 days after the start of surgery, after the end of CPB and after IMP initiation, between the *Octaplex* and FP groups.
- S10. Comparison of the incidence of intracerebral haemorrhage during the first 24 hours after start of surgery, after the end of CPB and after IMP initiation between the *Octaplex* and FP groups.
- S11. Comparison of the incidence of gastrointestinal haemorrhage during the first 24 hours after start of surgery, after the end of CPB and after IMP initiation between the *Octaplex* and FP groups.
- S12. Comparison of the incidence of surgical re-exploration for bleeding during the first 24 hours after start of surgery, after the end of CPB and after IMP initiation between the *Octaplex* and FP groups.
- S13. Comparison of the change in INR, from within 30 minutes before to within 60 minutes after the initiation of IMP administration, between the *Octaplex* and FP groups; INR reduction will be considered successful if the magnitude of the reduction is >1.0 or the post-treatment level drops below 1.5.
- S14. Comparison of the changes in other coagulation parameters, including PT, aPTT, fibrinogen activity, ROTEM EXTEM CT and MCF and platelets, from within 75 minutes before to within 75 minutes after the initiation of IMP administration, between the *Octaplex* and FP groups. For a given parameter, if there are multiple results in the window within 75 minutes before to initiation of IMP administration, the most recent result before IMP initiation will be used. If there are multiple results in the window within 75 minutes after the initiation of IMP administration, the earliest result after IMP administration will be used.
- S15. Comparison of time elapsed from initiation of the first dose of IMP to arrival at the ICU room between the *Octaplex* and FP groups. Patients in the ICU at the time of first dose of IMP will be excluded from this analysis.

The following analysis methods will be applied to the different endpoints, according to their data type:

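### At the SAP's own timing the 75-minute S14 pre-dose window reaches about 25 minutes into bypass, and nothing in S14 requires a post-bypass sample

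*SAP*

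**What the plan says.** S14 (SAP 10.3; item 14 in Protocol 3.1.2) compares the arms on the change in coagulation parameters other than INR, taken "from within 75 minutes before to within 75 minutes after the initiation of IMP administration". The SAP adds a selection rule: where a parameter has several results "in the window within 75 minutes before to initiation of IMP administration, the most recent result before IMP initiation will be used". The rule has work to do only when there is more than one result; a single result in the window is used as it stands. The general rule in SAP 7.1.1 is no stricter: "Baseline will be defined as the last value on or prior to the first IMP administration". Neither text mentions the end of CPB or protamine.

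On timing, SAP 6 (Canadian Study Sites) states: "The entire process from termination of CPB to administration of the blood products is around 50 minutes".

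On how the samples arise, Protocol 6 states: "Standard and point-of-care coagulation measures will be obtained as per usual clinical practice, ideally within 75 minutes before and after each IMP administration". Only two tests are mandatory at fixed times, under Protocol 7.3.6.2: "The haemoglobin and INR measurements will be performed at preestablished time points". The other S14 tests are collected from routine care as available.

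**The concern.** The trial treats bleeding after bypass, once heparin has been reversed. The ACT check in Protocol 3.2 and 6 governs the decision to dose; it does not decide which laboratory value is analysed. A sample drawn on pump describes a patient who is still heparinised and on the circuit. The change from that value to the post-dose value mixes any effect of the IMP with coming off bypass and receiving protamine. SAP 10.3 analyses S14 by ANOVA and states no adjustment for the baseline value, so any such shift passes straight into the change.

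The protocol recognises a related timing problem for one test. Footnote 3 to Figure 2 asks that point-of-care INR be taken more than 10–15 "minutes after protamine or results may be inaccurate". S14 has no timing safeguard of any kind.

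The window counts back from IMP initiation, and that moment may differ by arm. Protocol 1.1 says of plasma that "it requires ABO blood group compatibility matching and thawing, which can delay therapy", and that PCC can be given more quickly. With an earlier start, the same 75 minutes reach further back into bypass. At stake is the interpretation of secondary objective 9, the effect of PCC versus plasma on coagulation parameters.

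**Working it through.** The plan gives no figure for how many S14 baselines would be on-pump samples, so there is nothing to reproduce. The check is interval arithmetic on two stated times.

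**Inputs.** Window W = 75 min (SAP 10.3, S14). Interval from end of CPB to administration g = about 50 min (SAP 6), read here as the interval to IMP initiation. No spread and no arm-specific value is given.

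**Step 1. On-pump part of the window** = max(0, W - g).

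| g (min) | Source | On-pump minutes | Share of window |
|---|---|---|---|
| 40 | assumed | 75 - 40 = 35 | 47% |
| 50 | SAP 6 | 75 - 50 = 25 | 33% |
| 60 | assumed | 75 - 60 = 15 | 20% |
| 75 or more | assumed | 0 | 0% |

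**Step 2. Comparison with S13.** The INR endpoint has a 30-minute pre-dose window: max(0, 30 - 50) = 0 on-pump minutes. With the ±15 minutes in Protocol 6.1.3 the window is 45 minutes, which still gives 0 at g = 50, and 5 at an assumed g = 40.

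**Step 3. Patients whose window reaches bypass.** If g is assumed normal around 50 min, the share is P(g < 75) = Φ((75 - 50)/SD). It is 99% at SD 10, 89% at SD 20 and 80% at SD 30. These patients are exposed to the possibility. They are not the share whose baseline is an on-pump value, because a later pre-dose result replaces an earlier one.

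**Step 4. Effect on S14.** Let f be the share of an arm whose used baseline was drawn on pump. Let H be the amount by which the recorded change for a given parameter then moves, assumed equal in both arms.

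- Shift in an arm's mean change: f × H.
- Bias in the between-arm difference: (f_PCC - f_FP) × H.
- Added variance within an arm, if H is constant and unrelated to the rest of the change: f(1 - f)H². At f = 0.2 this is 0.16H².

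| f_PCC | f_FP | Between-arm bias |
|---|---|---|
| 0.3 | 0.3 | 0 |
| 0.3 | 0.2 | 0.1H |
| 0.3 | 0.1 | 0.2H |

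The values of f are illustrations. The documents give neither f nor H.

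**The case against.** The selection rule works in the plan's favour. With several results, the latest pre-dose one is used, and SAP 6 describes coagulation assays being reviewed in the 5–10 minutes around the order, within the post-bypass process. An on-pump value enters only when a parameter has no later pre-dose result. This stands, and it may keep f small. It does not remove the gap: the SAP does not say which assays are reviewed or when they were drawn, and no post-bypass repeat of each S14 test is required.

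The 50 minutes is an approximate figure, given to justify deferred consent. That also stands; the overlap disappears only at 75 minutes or more.

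A reader might infer that the S14 change simply reflects heparin reversal, or that a third of baselines are on pump. Neither follows. The 33% is a share of minutes, not of patients or results, and the documents do not say which S14 parameters heparin affects or by how much.

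A reader might also infer that the PCC correction of PT and aPTT is exaggerated. The same rule applies to both randomised arms, so bias needs unequal f. The protocol's remarks on plasma logistics make that possible, but no arm-specific start times are given; the 40 and 60 minute rows above are assumptions, not arm estimates.

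Footnote 3 concerns only point-of-care INR taken too soon after protamine. It does not support a fixed 15-minute exclusion for the S14 tests. Nor do the documents promise the time stamp such a rule would need: Protocol 4.2.1 lists protamine dose, and Protocol 6.1.3 lists no protamine time.

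**Conclusion.** The gap is real and minor. At the stated interval the S14 window extends about 25 minutes into bypass, and no condition in S14 or in the baseline definition excludes a sample from those minutes. Where such a sample is a patient's only pre-dose result for a parameter, the recorded change starts from a state other than the one being treated. The certain consequence, if any such baselines occur, is a distorted within-arm change with added noise, to the extent that the parameter differs between the on-pump and post-bypass states. Bias between arms is conditional on unequal frequency by arm. Its size cannot be derived from the documents.

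The conclusion rests on taking around 50 minutes as the typical interval to IMP initiation and on some patients lacking a later routine-care result. S14 is one of the secondary endpoints that the SAP says will be explored. The primary endpoint does not use these values, and the S13 pre-dose window lies after bypass at the stated timing.

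**What to change.** Amend the S14 text in SAP 10.3 as follows.

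1. Use the recorded CPB end time (Protocol 6.1.3) and the recorded sample time (Protocol 7.3.6.2) to flag every pre-IMP value drawn before the end of CPB. Report the number by arm and parameter.
2. Present S14, at least for PT and aPTT, with the pre-IMP value restricted to samples drawn after the end of CPB and within 75 minutes before IMP initiation. Show it beside the unrestricted 75-minute analysis.
3. Add a post-protamine condition only where a protamine time is recorded, with no fixed 15-minute rule. The end-of-CPB condition alone does not guarantee that heparin has been reversed, and the text should say so.

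The change needs SAP wording and programming, with no new data collection. Some patients will lose an S14 baseline in the restricted analysis. If on-pump baselines are commoner in one arm, that loss will be unequal too, which is why both analyses and the counts should be shown. Classification near the end of CPB will be slightly imprecise, because Protocol 7.3.6.2 allows an unrecorded draw time to be taken as laboratory receipt minus 10 minutes, or as the start of testing for ROTEM.

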This is a multicentre, randomised, active-control, prospective, Phase 3 study in adult cardiac surgery patients. Approximately 500 patients will be randomised at approximately 12 hospitals and the study will require approximately two years to complete.

The study will include adult (≥ 18 years old) patients who undergo cardiac surgery with cardiopulmonary bypass (CPB) and require coagulation factor replacement due to bleeding post-CPB and after adequate reversal of heparin with protamine (as assessed by the surgical staff based on clinical and laboratory criteria) during surgery, and who have a known (e.g., as indicated by INR) or suspected coagulation factor deficiency. Patients will be randomised to receive either 4-factor PCC (*Octaplex*) or FP when the blood bank/pharmacy receives the first order for coagulation factor replacement and determines patient eligibility with the study team based on the study inclusion and exclusion criteria. IMP will be administered once treatment indications are met. Patients will be treated according to their assigned group until the maximum dose of IMP is administered during the treatment period, which represents 24 hours after IMP initiation (defined as the start of IMP administration). If additional treatment is required after the maximum dose of IMP is administered or the treatment period has elapsed, patients in both groups will receive FP.

Other aspects of coagulation management will be according to a standardised transfusion algorithm. Measurements of INR and haemoglobin will be performed at

Name of Sponsor/Company: Octapharma AG	
Name of Investigational Product: Octaplex	Protocol Identification Code: LEX-211
Name of Active Ingredient: Prothrombin complex concentrate, human	Date of Final Protocol: 25-Aug-2023

preestablished time points, if not available already. No other aspects of care will be modified.

Name of Sponsor/Company: Octapharma AG	
Name of Investigational Product: Octaplex	Protocol Identification Code: LEX-211
Name of Active Ingredient: Prothrombin complex concentrate, human	Date of Final Protocol: 25-Aug-2023

Number of Patients:

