PCC offers a potential alternative to FP for treating bleeding cardiac surgery patients requiring coagulation factor replacement; however, no PCC product is currently approved for this indication in the United States. PCCs contain prothrombin and other enzymatic coagulation factors, the anticoagulant proteins C and S, and small amounts of heparin; thus, they are contraindicated in patients who are allergic to heparin or have a prior history of heparin-induced thrombocytopenia. PCCs are routinely defined as 3-factor (containing factors II, IX and X) or 4-factor (containing factors II, VII, IX and X) formulations [48]. PCCs are purified from human pooled plasma, which is fractionated into cryoprecipitate and cryoprecipitate-free plasma fractions through a process of slow thawing, then eluted from cryoprecipitate-free plasma [48]. The production of PCCs includes numerous pathogen inactivation steps using solvents, detergents, pasteurisation, nanofiltration and vapor-heated treatment [1, 48].

PCCs have several potential advantages over FP. Solvent/detergent treatment and filtering to remove pathogens substantially reduces the risk of transmission of infectious agents with PCCs. Indeed, a Consensus Conference recommended in 2007 that pathogen reduction technologies should be implemented to improve the safety of transfusion when they became available [49]. Unlike FP, PCCs do not require ABO compatibility matching or thawing, and can therefore be prepared and administered more quickly. PCCs are associated with a substantially lower risk of TRALI (due to pooling of the source donor plasma), and also a lower risk of TACO [38] as substantially lower volumes of PCC are required than with FP to achieve dose-equivalence for increasing thrombin generation (for example, in a 70-kg patient, a standard dose of 25 IU/kg PCC would be administered in a volume of 80 mL, whereas a standard dose of 15 mL/kg FP would be administered in a volume of 1000 mL) [47]. Finally, PCCs contain standardised levels of coagulation factors and thus have a more predictable therapeutic effect than FP, whose coagulation factor concentrations vary depending on the characteristics of the donor [50, 51].

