3.2 Overall Study Design and Plan

This is a multicentre, randomised, active-control, prospective, Phase 3 study in adult cardiac surgery patients. Approximately 500 patients will be randomised at approximately 12 hospitals (10 in Canada and two in the United States), and the study will require

approximately two years to complete. The study is planned to start in quarter 4, 2022 and to be completed in quarter 4, 2024.

The study will include adult (≥ 18 years old) patients who undergo cardiac surgery on CPB and require coagulation factor replacement due to bleeding post-CPB and after adequate reversal of heparin with protamine (as assessed by the surgical staff based on clinical and laboratory criteria) during surgery, and who have a known (e.g., as indicated by INR) or suspected coagulation factor deficiency. Patients will be randomised to receive either 4-factor PCC (*Octaplex*) or FP when the blood bank/pharmacy receives the first order for coagulation factor replacement and determines patient eligibility with the study team based on the study inclusion and exclusion criteria.

Following confirmation of eligibility, the technologist will randomise the patient to PCC or FP according to the randomisation and dosing schedule and prepare and release the IMP in a tamper sealed container. Operating room personnel will remain blinded until the decision to administer the IMP is made.

[figure not shown]
IMP can be administered if bleeding is severe enough to necessitate IMP (meaning at least a grade 2 level [moderate] bleeding according to the validated Bleeding Severity Scale [78]), heparin is adequately reversed (confirmed by the return of post-protamine activated clotting time [ACT] to within 10% of pre-pump ACT) and INR is ≥ 1.5 . IMP can also be administered if bleeding is severe enough to require urgent therapy, in which case treatment can be initiated irrespective of the INR value. Once the decision is made to administer the IMP, the administering clinician will break the seal on the container, carry out routine safety checks and initiate IMP administration according to the weight-based dosing recommendations.

The recommended initial dose for *Octaplex* will be 1500 IU for patients weighing ≤ 60 kg and 2000 IU for patients weighing >60 kg. The recommended initial dose for FP will be 3 U for patients weighing ≤ 60 kg and 4 U for patients weighing >60 kg.

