5.5 Preparation and Method of Administration

Each vial of *Octaplex* will be reconstituted with 20 mL or 40 mL WFI (as per the manufacturer's instructions) at room temperature (not more than 25°C). *Octaplex* dissolves at room temperature to an almost colourless and slightly opalescent solution within 10 minutes. It will not be used if it remains cloudy or contains particulates.

Octaplex will be administered intravenously, immediately after reconstitution as recommended, via free-flowing IV syringe injection. *Octaplex* should not be mixed with other medicinal products or crystalloid intravenous solutions.

FP will be thawed and administered according to the local standard.

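### S15 times ICU arrival from the start of IMP, a post-randomisation moment the assigned product can shift; a comparison from randomisation or end of CPB should be added

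*SAP*

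**What the plan says.** SAP section 10.3 (S15) specifies "Comparison of time elapsed from initiation of the first dose of IMP to arrival at the ICU room", then adds: "Patients in the ICU at the time of first dose of IMP will be excluded from this analysis". The exclusion appears only there; Protocol section 3.1.2 and SAP section 5.2 give the endpoint without it. S15 is analysed with the continuous variables, by group differences, 95% confidence intervals and an ANOVA F-test. No adjustment for time before IMP start is stated.

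The protocol synopsis (Study Design) fixes the meaning of the clock start: "24 hours after IMP initiation (defined as the start of IMP administration". Randomisation comes earlier. Under Protocol section 3.2, once the order has arrived and eligibility is confirmed, "the technologist will randomise the patient to PCC or FP according to the randomisation and dosing schedule and prepare and release the IMP".

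On preparation, Protocol section 1.1 says of plasma that "it requires ABO blood group compatibility matching and thawing, which can delay therapy", and of the comparator: "Unlike FP, PCCs do not require ABO compatibility matching or thawing, and can therefore be prepared and administered more quickly".

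Several other secondary endpoints (S3 to S5 and S7 to S12) use end of CPB as an origin, alone or alongside others. S15 has IMP initiation only.

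**The concern.** A randomised comparison of durations needs a starting point that the assigned treatment cannot move. S15 starts at an event that follows both randomisation and preparation of the product, and the protocol itself expects preparation to differ between products. Any extra wait for plasma is left out of plasma's time. Meanwhile, whatever surgical work continues during that wait shortens the time still to run once plasma begins.

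The exclusion acts on the same moment. A patient is dropped when IMP starts after ICU arrival, so an arm that starts later can lose more patients.

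At stake is the reading of secondary objective 10. The quicker availability that the protocol names as an advantage of PCC falls outside S15's window, and no other planned analysis of time to ICU captures it.

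**Working it through.** **Inputs from the documents**
- Clock start and stop, exclusion and F-test: SAP section 10.3.
- IMP initiation is the start of administration: protocol synopsis, Study Design.
- Randomisation precedes preparation: Protocol section 3.2.
- Product-dependent preparation: Protocol section 1.1.
- Group size of 205 evaluable patients (410 in total): Protocol section 3.3.1.5. This was set for the primary endpoint and is used here only as a group size.

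**Not in the documents:** the mean extra delay for plasma, d, and the standard deviation of S15. I assume d from 5 to 30 minutes and SDs of 45, 60 and 90 minutes. The plan states no figure for S15, so there is none to reproduce.

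**Step 1: the identity.** For one patient, let T be the time from a common origin (randomisation or end of CPB) to ICU arrival, and W the time from that origin to IMP start. Then

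S15 = T − W.

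Taking means, plasma minus PCC, with ΔT the difference in T and d the difference in W:

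ΔS15 = ΔT − d.

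**Step 2: what S15 reports, with d = 20 minutes assumed**
- Equal arrival from the common origin, ΔT = 0: ΔS15 = 0 − 20 = −20. Plasma appears 20 minutes faster.
- Plasma arrives 20 minutes later, ΔT = 20: ΔS15 = 20 − 20 = 0. A real difference disappears.
- Plasma arrives 30 minutes later, ΔT = 30: ΔS15 = 30 − 20 = +10. The difference is understated.

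With the clock at the common origin the three results are 0, 20 and 30, whatever d is.

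**Step 3: could the first case reach significance?** With 205 per arm the standard error is SD × √(2/205). For SD 60 this is 60 × 0.0988 = 5.93 minutes. At d = 10 the chance of a two-sided 5% result favouring plasma is Φ(10/5.93 − 1.96) = Φ(−0.27) = 39%. The same formula gives the table below, where ΔT = 0 throughout.

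| Assumed SD (min) | d = 5 | d = 10 | d = 15 | d = 20 | d = 30 |
|---|---|---|---|---|---|
| 45 | 20% | 61% | 92% | 99% | >99% |
| 60 | 13% | 39% | 72% | 92% | >99% |
| 90 | 8% | 20% | 39% | 61% | 92% |

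Simulating the F-test (4,000 trials, equal order-to-ICU time with SD 60) gave a mean difference of −9.9 minutes with 38% significant at d = 10, and −20.1 minutes with 93% significant at d = 20. These figures show sensitivity under assumed inputs and do not forecast the trial's result.

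**Step 4: the exclusion.** A patient is dropped when W exceeds T, because S15 would be negative. With the same distribution of T in both arms and later W for plasma, more plasma patients can meet that condition. The documents give no count, so the imbalance cannot be sized.

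**The case against.** The strongest reply is that S15 measures what objective 10 asks for. Protocol section 2.2 and SAP section 3.2 both word that objective as time from IMP initiation, and the endpoint agrees in both documents. This stands: the choice of clock is not a conflict between protocol and SAP, and S15 remains a legitimate description of time after treatment starts. It does not make the contrast a fair one between randomised groups, since patients may enter the clock at different points in the operation by arm.

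A reader might go further and infer that S15 will report plasma as faster, perhaps by 10 to 30 minutes. The documents do not support that.
- Section 1.1 says only that matching and thawing can cause delay, and it gives no minutes.
- The roughly 50 minutes in SAP section 6 covers the whole path from end of CPB to administration, in an argument about consent. It says nothing about a difference between arms.
- PCC also needs preparation: it "dissolves at room temperature to an almost colourless and slightly opalescent solution within 10 minutes" (Protocol section 5.5).
- After delivery, both products wait on the same conditions, beginning with "IMP can be administered if bleeding is severe enough to necessitate IMP" (Protocol section 3.2). That wait may absorb part of any delay.
- Section 1.1 also says that the volume of plasma may slow haemostatic control, which would lengthen S15 for plasma.

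The exclusion is also defensible within the present clock, because the patients it removes would have zero or negative times. First doses in the ICU should be uncommon: orders come from the operating room, and Protocol section 3.3.1.6 has the seal broken there just before infusion.

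Finally, a clock from end of CPB with no exclusion counts some ICU arrivals that preceded any IMP, and adds time unrelated to the product. That is a reason to keep the present S15 alongside the new comparison, as a description. It is not a reason against adding the comparison, because waiting for the product is part of each randomised strategy.

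**Conclusion.** The concern holds as a design weakness of one exploratory secondary endpoint. S15 starts at a post-randomisation time that the protocol expects to depend on the product, so a difference in S15 equals the difference in ICU arrival from a common origin minus the difference in IMP start. If arrival is equal, the result is d minutes in plasma's favour.

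The size of d is unknown, and the 5 to 30 minutes used above is an assumption. Because slower haemostasis after plasma begins could act the other way, the net direction is not predictable, and S15 could show a difference where there is none or hide a real one. The exclusion could add an imbalance of unknown, probably small, size.

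The preparation effect taken alone runs against the sponsor's product. S15 lies outside the confirmatory testing in SAP section 10.2, so the primary conclusion is unaffected. This is a cheap improvement.

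**What to change.** Add to S15, in SAP section 10.3, a between-arm comparison of time from randomisation to ICU arrival in all FAS patients, with no exclusion for being in the ICU at first dose. End of CPB is a workable alternative origin. Base the between-arm conclusion on time to ICU on this comparison.

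Keep time from IMP initiation, with its exclusion, as a descriptive figure matching objective 10. Beside it, report by arm the time from randomisation (or end of CPB) to IMP initiation and the number of patients excluded.

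The cost is one extra analysis and an aligned line in the protocol endpoint. CPB end time and IMP start time are on the collection list in Protocol section 6.1.3, and S15 already needs ICU arrival time. Randomisation time is not on that list, so confirm that it is recorded before choosing it. Make the change before database lock.
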